## HYPOTHESIS

Patients with severe chest trauma who undergo SSRF will have decreased rates of opioid consumption as measured in morphine milligram equivalents per day. Patients with severe chest trauma who undergo SSRF will also have improved health status (as measured by the EuroQOL-5D-5L) at 30 days and 3 months, earlier return to work or normal physical activity, and decreased time from injury to resolution of chest wall pain.

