### Secondary Outcomes (Clinical Metrics):

- Mortality
- Incidence of respiratory failure requiring mechanical ventilation > 24 hours
- Incidence of tracheostomy
- Inpatient incidence of pneumonia
  - >10,000 cfu/mL on bronchioalveolar lavage -or-
  - Clinical diagnosis of pneumonia with subsequent antibiotic treatment
- Utilization of regional anesthesia (binary outcome)
- Opioid usage (continuous and binary)
- Lengths of stay
  - Hospital-free days (= 30 minus number of hospital days; in-hospital death = 0)
  - Ventilator-free days (= 30 minus number of ventilator days; in-hospital death = 0)

- ICU-free days (= 30 minus number of intensive care unit days; in-hospital death = 0)
- Re-intervention rates for surgical complications, including bleeding, seroma, and surgical site infection

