**Secondary Outcomes (Patient-Centered Outcomes):**

- Health status at 30 days, 3 months, and 6 months as measured by the EuroQol-5D-5L
- Time from injury to return to work or usual activity (days)
- Time from injury to resolution of pain (days)

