### **STATISTICS**

The primary and secondary outcomes will be analyzed on an intention to treat basis, though a per protocol analysis will also be performed. Demographics, injury characteristics, and eligible rib fracture patterns will be reported. Subgroup analyses will be stratified *a priori* by unit of admission. All statistical analyses will be performed using STATA® (version 15.1; StataCorp; College Station, TX) and R© (The R Foundation) commercially available software.

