### Frequentist Analysis

Generalized linear models (GLMs) will be used to analyze all outcomes and will include treatment group and unit of admission (stratifying variable) as covariates. For LOS outcomes, negative binomial or zero-inflated negative binomial (for outcomes with large number of zeros; *e.g.*, ventilator days, ICU days) regression models will be used. Binary outcomes will be analyzed with log binomial regression models to estimate relative risks (RRs). For longitudinal outcomes, we will use mixed models including treatment group, time, and center as covariates and a random intercept (and slope if needed) for subject. We will report RRs or group differences and 95% confidence intervals for all outcomes.

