### Bayesian Analysis

Bayesian statistics will be used to detect differences in treatment effects overall and in different patient subgroups. Models will be the same as in frequentist analyses (*i.e.*, GLMs with same covariates). For LOS outcomes, neutral priors centered at RR of 1.0 with 95% prior interval of 0.33-3.0 (0.5-2 for binary outcomes) will be used for the treatment effect (in the log RR scale, a Normal distribution with mean of 0 and variance of 0.57). A Normal (0, 10) prior will be used for the intercept term. Normal (0, 1) will be used for all other variables in the model. For sensitivity analyses, we will specify enthusiastic and skeptical priors based on the best published evidence (*i.e.*, Cochrane review). For all Bayesian analyses, we will report posterior medians and 95% credible intervals for group comparisons and probabilities of benefit or harm from the intervention.

**Feasibility:** From unpublished historical data from the Red Duke Trauma Institute from the calendar year 2017, approximately 300 patients matched these enrollment criteria. Accordingly, enrollment of 150-250 patients is expected over the course of the study.

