Opioid prescription at discharge? (yes/no)

Tramadol prescription at discharge? (yes/no)

Ventilator days

ICU days

Hospital days

Did the patient survive to 1 month? (yes/no)  
Was the patient able to answer questions at 1 month? (yes/no)  
Did the patient consent to be asked questions at 1 month? (yes/no)

Did the patient survive to 3 months? (yes/no)  
Was the patient able to answer questions at 3 months? (yes/no)  
Did the patient consent to be asked questions at 3 months? (yes/no)

Did the patient survive to 6 months? (yes/no)  
Was the patient able to answer questions at 6 months? (yes/no)  
Did the patient consent to be asked questions at 6 months? (yes/no)

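### The plan gives no rule for death in the EQ-5D-5L analysis, so by default the mixed model compares survivors rather than the randomised groups

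*Combined protocol and SAP*

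**What the plan says.** The patient-centered secondary outcomes include "Health status at 30 days, 3 months, and 6 months as measured by the EuroQol-5D-5L". The Hypothesis section expects "improved health status (as measured by the EuroQOL-5D-5L) at 30 days and 3 months" with SSRF. The Follow Up section and Appendix A give the same three time points; neither lists a baseline questionnaire.

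The Frequentist Analysis section states: "For longitudinal outcomes, we will use mixed models". The specification in full is: "we will use mixed models including treatment group, time, and center as covariates and a random intercept (and slope if needed) for subject". That sentence does not name EuroQol, but EQ-5D-5L is the scale the plan measures repeatedly. The Bayesian Analysis section adds: "Models will be the same as in frequentist analyses". The Statistics section states: "The primary and secondary outcomes will be analyzed on an intention to treat basis".

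Death is handled elsewhere. Each of the three free-day outcomes scores in-hospital death as 0, for example "Ventilator-free days (= 30 minus number of ventilator days; in-hospital death = 0". Mortality is a separate secondary outcome. Appendix B records survival at 1, 3 and 6 months, for example "Did the patient survive to 3 months? (yes/no". Nothing gives a health-status value after death, defines a survivor estimand, or plans a sensitivity analysis for death. The Limitations section provides only for examining dropouts if losses are large, and does not mention death.

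**The concern.** A random-intercept model uses the scores that exist. Without a baseline, a patient who dies before day 30 has none and leaves the analysis. A patient who dies later contributes the earlier scores, and the likelihood treats the rest as values that existed but were not seen.

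The arms then being compared are the survivors of each arm, and randomisation does not protect that comparison if treatment affects who survives. If one arm keeps more of the sickest patients alive, their low scores pull down that arm's mean, while in the other arm the same kind of patient is absent. The effect works in either direction: it counts against whichever arm has fewer deaths. At stake are the direction and interpretation of an outcome that forms part of the study hypothesis, although not the primary outcome, hospital length of stay.

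**Working it through.** The documents give no EQ-5D effect, standard deviation, power or mortality rate, so there is no plan figure to reproduce. The group sizes come from the Sample Size Calculation section (75 per arm at 150 patients, 125 at 250). Every other input below is an assumption.

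**Closed form at a single visit, all deaths before it.** Let pc and ps be mortality under usual care and SSRF, with pc ≥ ps. Patients who survive under either treatment have mean 0.70 in both arms; patients alive only because of SSRF have mean 0.30.

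- SSRF survivor mean: m = [(1 - pc) × 0.70 + (pc - ps) × 0.30] / (1 - ps)
- Survivors-only difference: m - 0.70
- Difference with death = 0: (1 - ps) × m - (1 - pc) × 0.70

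For 6% v 2%: m = (0.94 × 0.70 + 0.04 × 0.30) / 0.98 = 0.670 / 0.98 = 0.684. Survivors-only: 0.684 - 0.70 = -0.016. Death = 0: 0.670 - 0.658 = +0.012.

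With an assumed SD of 0.25, the standard error at 75 per arm is 0.25 × √(2/75) = 0.041.

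| Mortality, usual care v SSRF | Expected deaths at 75 per arm | Survivors only | Death = 0 | Survivors-only shift in SE |
|---|---|---|---|---|
| 5% v 4% | 3.75 v 3 | -0.004 | +0.003 | 0.10 |
| 6% v 2% | 4.5 v 1.5 | -0.016 | +0.012 | 0.40 |
| 10% v 4% | 7.5 v 3 | -0.025 | +0.018 | 0.61 |

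At 125 per arm the SE is 0.25 × √(2/125) = 0.032 and the shifts are 0.13, 0.52 and 0.79 SE.

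**Equal mortality.** If mortality is p in both arms and survivors differ by d, scoring death as 0 gives (1 - p) × d. The two analyses agree exactly only when d = 0; otherwise the death-scored difference is slightly smaller.

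**Check with the planned type of model.** A random-intercept model was fitted to 400,000 simulated patients per arm with three visits. SSRF had no effect on any individual's score, and deaths were concentrated in the frailest (assumed mean 0.70 at the first visit, between-patient SD 0.20, within-patient SD 0.10). Results are SSRF minus usual care, observed visits only, then with death = 0:

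- 6% v 3%: -0.0105, then +0.0124 if all deaths precede day 30; -0.0059, then +0.0103 if half come after the 30-day visit.
- 10% v 5%: -0.0154, then +0.0239; or -0.0086, then +0.0190.
- 15% v 5%: -0.0291, then +0.0500; or -0.0157, then +0.0412.
- 5% v 5%: within 0.0003 of zero in both analyses.

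The SE at 125 per arm is about 0.027, so with unequal mortality the survivors-only shift runs from 0.0059/0.0267 = 0.2 SE to 0.0291/0.0278 = 1.0 SE.

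**The case against.** The strongest reply is that the effect is conditional and probably small. The documents give no mortality rate, the hypothesis claims no mortality benefit, and the exclusion criteria remove severe brain injury, spinal cord injury, heart failure and oxygen-dependent lung disease, so deaths may be few. The larger gaps in the table assume that SSRF cuts mortality by 60% or more. At 5% v 4% the two analyses differ by only 0.007, under 0.2 SE. In none of the table's scenarios could either sign be told from zero at 75 per arm. All of this stands, and it limits the weight of the point.

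Three stronger readings are tempting, and the documents do not support them.

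- A reader might infer that the plan has decided to treat deaths as missing. It has not said so; that is what follows by default from its silence.
- A reader might infer that SSRF will wrongly look harmful on health status. That needs a mortality difference in its favour, concentrated in sicker patients, which nothing in the documents establishes.
- A reader might infer that death = 0 is the only valid main analysis. The documents name no index or value set, and survivor results shown beside mortality are a legitimate summary if labelled as such. The distance between the two columns is a difference between two estimands, so it should not be read as bias.

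The reply does not supply the missing rule. The Bayesian analysis will report probabilities of benefit or harm, with no significance threshold to absorb a shift of part of a standard error.

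**Conclusion.** The point holds as a worthwhile, inexpensive improvement to a secondary analysis. With no death rule and no baseline score, the model as written leaves out patients who die before day 30 and extrapolates later deaths, which does not match the intention-to-treat statement. When mortality differs and falls on the sickest, the survivors-only difference shifts against the arm with fewer deaths. On the closed-form assumptions the shift is 0.004 to 0.025, about 0.1 to 0.6 SE at 75 per arm, and scoring death as 0 gives the opposite sign. These sizes rest on assumed mortality, scores and SD. With equal mortality and no difference among survivors there is nothing to correct. The point does not touch the primary outcome.

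**What to change.** In the Frequentist and Bayesian Analysis sections:

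1. Name the health-status score to be analysed. Appendix A collects five items and a 0-100 rating, and the plan does not say which enters the model.
2. Prespecify an analysis of all randomised patients that gives every planned visit after death a fixed worst value (for example 0, in line with the free-day outcomes), using the survival items in Appendix B. The rule should cover death at any time up to 6 months, not only in hospital.
3. Report this beside the mixed model, labelled as survivors-only, and beside mortality.

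The cost is mainly wording, plus the choice of a value set if an index is used. No new data item is needed. However, the Data Collection section ends clinical data at discharge or 30 days, so later vital status may depend on follow-up contact and should be actively ascertained. The downside is that the death-scored result mixes survival with quality of life and slightly dilutes a pure quality-of-life effect, which is why both results should be shown. The choice should be fixed before outcome data by arm are seen.

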## STUDY DESIGN

Single center, pragmatic, prospective, randomized clinical trial with a parallel observational arm to compare usual care alone to usual care plus early surgical stabilization of rib fractures. Screening will occur at admission. Randomization will occur after informed consent has been obtained. A 1:1 allocation ratio using a permuted block design of 4 or 6 will be used to ensure equal number of patients in each group. Randomization will be performed using the randomization module in REDCap and stratified by unit of admission. If randomized to SSRF, the procedure should occur as early as possible after admission (given competing/concomitant injuries), ideally within 72 hours. Study enrollment will occur over 18 months. Total study duration including follow-up = 24 months.

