### Randomization:

Eligible subjects who have consented to participate will be randomized into one of two groups: 1) Control arm or 2) Intervention arm. The two arms are described in detail below. A 1:1 allocation ratio using a permuted block design of 4 or 6 will be used to ensure equal number of patients in each group. Randomization will be performed using the randomization module in REDCap and stratified by unit of admission.

Control Arm: Control patients will receive usual care per our established institutional guidelines, consisting of pulmonary toilet, lung volume expansion exercises, and a multimodal approach to oral pain medication management. For severe pain not responding to oral therapy, intravenous narcotics, lidocaine, or ketamine may be added. Regional analgesia techniques such as epidural analgesia, paravertebral analgesia, and intercostal nerve blockade may also be considered. The pain medication regimen is deescalated as pulmonary status and pain control allow.

(<https://med.uth.edu/surgery/files/2017/06/Chest-Management-of-Multiple-Rib-Fractures-2013.pdf>)

For patients who fail all of these therapies and desire to proceed with SSRF, the procedure may be offered late, as salvage therapy.

Intervention Arm: The intervention will consist of early surgical stabilization of the fractured ribs plus usual care. If randomized to SSRF, the procedure should occur as early as possible (given the patient clinical status and need for more emergent procedures), ideally within the first 72 hours of hospital admission. Since stabilization of all fractures may not be possible due to anatomic exposure (e.g., the first, second, and third ribs may be difficult to access due to their location), the surgery must stabilize at least one true rib (ribs 1-7). Stabilization of the true ribs is considered more critical due to their greater contribution to chest wall volume and mechanical respiratory function.

Observation Arm: Patients refusing consent to randomization will be invited to participate in the observational arm. Patients selecting this option will be asked to complete the same assessments as the randomized groups.

Equipment: In order to maintain a pragmatic approach, surgical stabilization will be performed using any commercially available internal rib fixation system, at the discretion of the operating surgeon.

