#### Appendix B. List of Data Elements to be Collected

Study number

Gender (male/female)

Age

Race (white, black, Hispanic, Asian, other, unknown)

Trauma type (blunt/penetrating)

Mechanism (MVC, MCC, fall, auto pedestrian, ATV, assault, crush, GSW, stab, other)

Date/time of injury

PH vital signs

Transfer? (yes/no)

ED arrival date/time

ED vitals

ED CBC

ED BMP

ED rTEG

ED lactate

ED base excess

Unit of admission

Randomization group (SSRF/usual care)

R 1st rib fx?

Segmental?

Displaced?

R 2nd rib fx?

Segmental?

Displaced?

R 3rd rib fx?

Segmental?

Displaced?

R 4th rib fx?

Segmental?

Displaced?

R 5th rib fx?

Segmental?

Displaced?

R 6th rib fx?

Segmental?

Displaced?

R 7th rib fx?

Segmental?

Displaced?

L 1st rib fx?

Segmental?

Displaced?

L 2nd rib fx?

Segmental?

Displaced?

L 3rd rib fx?

Segmental?

Displaced?

L 4th rib fx?

Segmental?

Displaced?

L 5th rib fx?

Segmental?

Displaced?

L 6th rib fx?

Segmental?

Displaced?

L 7th rib fx?

Segmental?

Displaced?

Radiographic flail segment? (yes/no)

Flail chest? (yes/no)

Right clavicle fx? (yes/no)

Left clavicle fx? (yes/no)

Right scapula fx? (yes/no)

Left scapula fx? (yes/no)

Mechanical ventilation immediately prior to SSRF? (yes/no)

Tracheostomy prior to SSRF? (yes/no)

Clinical suspicion of PNA prior to SSRF? (yes/no)

Chest tube prior to SSRF? (yes/no)

Date/time of SSRF

Time from admission to SSRF (hours)

Procedure time (min)

Hardware system (Synthes/KLS Martin)

Right ribs stabilized by SSRF

1 (yes/no)

2 (yes/no)

3 (yes/no)

...

Left ribs stabilized by SSRF

1 (yes/no)

2 (yes/no)

3 (yes/no)

...

VATS? (yes/no)

Thoracotomy? (yes/no)

w-RTS

ISS

AIS head/neck

AIS face

AIS chest

AIS abdomen

AIS extremity

AIS external

Regional analgesia for rib fxs? (yes/no)

If yes, what kind? (epidural, paravertebral, intercostal, serratus plane, other)

Post-SSRF PNA? (yes/no)

Post-SSRF hardware infection? (yes/no)

Post-SSRF seroma requiring intervention? (yes/no)

Post-SSRF hematoma requiring intervention? (yes/no)

Post-SSRF hardware failure? (yes/no)

Post-SSRF need for hardware removal for any reason? (yes/no)

Post-SSRF SSI? (yes/no)

Superficial? (yes/no)

Deep? (yes/no)

Organ space? (yes/no)

DVT? (yes/no)

PE? (yes/no)

Discharge date/time

Discharge disposition (home, rehab, SNF, LTAC, transfer to other hospital, level 1 psych, morgue, other)

Total opioid use (MME)

MME/day

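### The longitudinal mixed model adjusts for center, a constant in this single-center trial, and does not list unit of admission, in conflict with the plan's own covariate rule and its stratified randomization

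*Combined protocol and SAP*

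**What the plan says.** The Study Design section describes a "Single center, pragmatic, prospective, randomized clinical trial with a parallel observational arm". On allocation it says "Randomization will be performed using the randomization module in REDCap and stratified by unit of admission", and the Randomization section adds "A 1:1 allocation ratio using a permuted block design of 4 or 6 will be used". No other stratification factor is named.

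The Frequentist Analysis section contains two covariate statements:

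- The opening rule: "Generalized linear models (GLMs) will be used to analyze all outcomes and will include treatment group and unit of admission (stratifying variable) as covariates".
- The rule for longitudinal outcomes: "we will use mixed models including treatment group, time, and center as covariates", with a random intercept for subject and a random slope if needed.

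The patient-centered secondary outcomes include "Health status at 30 days, 3 months, and 6 months as measured by the EuroQol-5D-5L", the repeated measure to which the second rule applies. The Bayesian Analysis section reuses the frequentist models and their covariates. Appendix B lists "Unit of admission" among the data elements and has no center variable.

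**The concern.** In a single-center trial, center takes one value. It cannot be separated from the intercept, so the model cannot be fitted with the covariates as listed. The analyst must drop center or replace it, and the plan does not say which. If it is dropped, nothing in the model reflects how patients were allocated.

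That matters because stratified blocks balance unit of admission between the arms, so differences between units contribute almost nothing to the sampling error of the treatment effect. A model without unit still counts those differences as patient-to-patient noise, and the reported standard error is then larger than the true spread of the estimate. At stake are the width of the health-status intervals and the power of that comparison. There is also a prespecification issue: two covariate sets can be defended from the text, and the choice should not be left until data are in hand.

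**Working it through.** **1. The plan's own figures.** The plan gives no power or precision figure for health status. Its only power statements concern hospital length of stay: 85% at 150 patients (10 v 7 days) and 89% at 250 (10 v 7.5 days), two-sided alpha 0.05. A gamma fit to a median of 10 and IQR of 6-15 gives mean 11.35 and shape k = 2.51. For a negative binomial Wald test with n per arm, SE² = (1/n)(1/μ₁ + 1/k + 1/μ₂ + 1/k).

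- n = 75, rate ratio 0.70: SE² = (0.088 + 0.399 + 0.126 + 0.399)/75 = 0.0135, SE = 0.116. Power = Φ(0.357/0.116 − 1.96) = 86.7%.
- n = 125, rate ratio 0.75: SE² = (0.088 + 0.399 + 0.117 + 0.399)/125 = 0.0080, SE = 0.0896. Power = Φ(0.288/0.0896 − 1.96) = 89.4%.

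Both are within two points of the stated values. They do not depend on the mixed model, so this point leaves them untouched.

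**2. Effect of omitting unit of admission.** Let R² be the share of the within-arm variance of a patient's mean score explained by unit. The documents do not give it, so the values below are assumptions. Under stratified blocked randomization and a linear model:

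- ratio of reported to true SE: r = 1/√(1 − R²)
- actual type I error: 2[1 − Φ(1.96 r)]
- power that would be 80% with unit in the model: Φ(2.80 − 1.96 r)

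Example, R² = 0.10: r = 1/√0.90 = 1.054. Type I error = 2[1 − Φ(2.066)] = 3.9%. Power = Φ(2.80 − 2.066) = 76.9%.

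| R² (assumed) | Interval too wide by | Type I error | Power instead of 80% |
|---|---|---|---|
| 0 | 0% | 5.0% | 80.0% |
| 0.02 | 1.0% | 4.8% | 79.4% |
| 0.05 | 2.6% | 4.4% | 78.5% |
| 0.10 | 5.4% | 3.9% | 76.9% |
| 0.20 | 11.8% | 2.8% | 72.9% |

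**3. Simulation check.** 4,000 trials per setting, three units (assumed; the documents state no number), blocks of 4 or 6, analysis of each patient's mean, complete data, no treatment effect. The Monte Carlo error on a 5% rate is √(0.05 × 0.95/4000) = 0.3 points.

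| N | R² | True SD of estimate | Mean SE, unit omitted | Mean SE, unit included | Type I error, omitted / included |
|---|---|---|---|---|---|
| 150 | 0 | 0.164 | 0.163 | 0.163 | 5.0% / 5.0% |
| 150 | 0.10 | 0.155 | 0.163 | 0.155 | 4.2% / 5.2% |
| 150 | 0.20 | 0.146 | 0.163 | 0.146 | 3.0% / 5.0% |
| 250 | 0.20 | 0.113 | 0.126 | 0.113 | 3.1% / 5.2% |

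The ratio of the two mean SEs was 1.000, 1.054, 1.118 and 1.119 in these four rows, as the formula predicts. The true spread of the estimate is virtually the same with or without unit. Only the reported SE changes.

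**4. What R² refers to.** It is the share of variance of the patient's mean over three visits. If unit's share were stated for the random-intercept variance instead, the effect would be smaller. With an assumed within-patient correlation of 0.5, the variance of the mean is 0.5 + 0.5/3 = 0.667, so a 10% share of the intercept variance is 0.05/0.667 = 7.5% of it (4.0% too wide), and a 20% share is 15% (8.5% too wide).

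**The case against.** The strongest reply is that the plan already gives the right covariate. The opening rule covers all outcomes, so center is most naturally read as a slip for unit of admission, and a constant covariate would be noticed at the first model fit. This has real force. A reader might infer that the health-status analysis is bound to ignore the stratification, and the full text does not support that. It supports only a conflict between two sentences. The conflict is still worth removing: the opening rule speaks of generalized linear models, while the later, more specific sentence gives mixed models a covariate list of their own.

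A second reply is that the loss may be nil. This also stands. It is zero if unit does not predict health status, and nothing in the documents shows how strongly it does.

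A third is that the Bayesian section's reference to the same covariates points most directly to the generalized linear model rule, which already contains unit. That is fair, so confirmation is enough there.

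**Conclusion.** The inconsistency is certain from the text; its numerical consequence is conditional. Intervals are too wide only if the mixed-model sentence is applied literally and unit of admission predicts EuroQol-5D-5L scores. For an assumed R² of 0.02 to 0.10 the excess width is about 1 to 5%, and at 0.20 it is about 12%. These figures assume a linear model, stratified blocks and complete follow-up.

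Three stronger readings are tempting but unsupported. A reader might infer that the health-status intervals will be too wide; the documents give no basis for a non-zero R², let alone a large one. A reader might infer that the trial's conclusions are at risk; the omission does not bias the treatment estimate, it makes the test conservative, and the length-of-stay model includes unit under the opening rule. A reader might treat the EuroQol-5D-5L as the leading patient-centered outcome; the protocol lists it with return to work or usual activity and resolution of pain, without ranking them.

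Severity is minor to moderate.

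**What to change.** In the mixed-model sentence of the Frequentist Analysis section, replace center with unit of admission, identified as the stratifying variable. In the Bayesian Analysis section, add a clause confirming that any longitudinal model uses the same covariate.

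The cost is a few words before analysis begins. The variable is already in Appendix B, so no new data are needed. In the simulation with three units, including it cost no precision even when it had no association with the outcome (SE ratio 1.000).
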